11.3.2 Secondary Endpoints

- 1) Histological staining for Treg cells in renal biopsy tissue between baseline and 3 month protocol biopsy
- 2) Incidence of delayed graft function, defined as the need for dialysis within 1 week post-transplant
- 3) Diabetic control between baseline and month 3 using change in HbA1c measurement
- 4) Dose of other anti-diabetic medication between baseline and month 3 (descriptive)
- 5) Safety endpoints: i.e. number of hypoglycaemic episodes (descriptive)
- 6) Insulin resistance: HOMA IR measurement at month 3
- 7) Graft function: (eGFR) at month 3
- 8) Episodes of acute rejection (defined as biopsy proven acute rejection)
- 9) Episodes of opportunistic infections: bacterial and viral (descriptive)

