11.4 Exploratory or Tertiary Endpoints/outcomes

- 1) 12-month graft function (eGFR) and diabetic control (HbA1c; medication review) to assess legacy effect (potential follow up publication)
- 2) Differences in other peripheral T cell populations, measured by FACS analysis
- 3) Histological staining for Treg cells in any renal biopsy taken for clinical indications between baseline and month 3 protocol biopsy
- 4) Differences in the functional phenotype of the Treg cells

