19.0 Statistical and Data Analysis

19.1 Sample size calculation

n=25 in each arm. This is a pilot/exploratory study: the numbers were chosen as this was felt to be feasible given the resources of the site, and will enable generation of data for a larger scale trial should the results of this pilot be encouraging.

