- Hypertension (yes/no, categorical)
- Heart failure (yes/no, categorical)

Pregnancy test

• Pregnancy test negative (either serum or urine) (yes/no, categorical)

Transplant details

- Cold ischaemia time in hours (continuous)
- Warm ischaemic rime minutes (continuous)
- Donor age (continuous)
- ECD (yes/no, categorical)
- CMV mismatch (yes/no, categorical)
- HLA mismatch (categorical)

Medication

Each medication will be recorded as name/dose/start date (categorical)

Biochemical Parameters

- Fasting c-peptide (continuous)
- Fasting cholesterol (continuous)
- Haemoglobin (continuous)
- Serum sodium (continuous)
- Serum potassium (continuous)
- Serum urea (continuous)
- Serum creatinine (continuous)
- eGFR (CKD-EPI formula, continuous)
- Serum albumin (continuous)
- Serum alkaline phosphatase (continuous)
- Serum bilirubin (continuous)
- Serum alanine aminotransferase (continuous)
- Serum calcium (continuous)
- Serum phosphate (continuous)
- C-reactive protein (continuous)
- Glucose (continuous)
- Haemoglobin A1C (DCCT aligned; continuous)
- Peripheral Treg Cell number (interval)
- HOMA IR (continuous)

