19.5 Primary outcome analysis

The endpoint data will be analysed on an ITT basis, with no subgroup analysis using unpaired parametric and non-parametric analysis as necessary, comparing the

change in mean Treg cell number between baseline and month 3 between the 2 groups.

Continuous variables will be tested for normality using D'Agostino-Pearson normality test. Mean (standard deviation), median (interquartile ranges) will be displayed along with max-min point estimate and confidence intervals. Statistical analysis will be by student t-test (unpaired) or Mann-Whitney U test.

Categorical data will be analysed by Chi Square test.

Statistical significance considered if P-value <0.05.

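### The supplied text plans no baseline adjustment of month-3 HOMA-IR although baseline HOMA-IR is collected: a cheap gain in precision, of uncertain size

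*Combined protocol and SAP*

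**What the plan says.** **Endpoints.** Section 11.3.2 lists "Insulin resistance: HOMA IR measurement at month 3" and "Graft function: (eGFR) at month 3". Section 11.4 adds "12-month graft function (eGFR) and diabetic control" as exploratory. The summary in section 11.5 repeats HOMA-IR at month 3 and eGFR at 3 and 12 months. All are follow-up values. HbA1c and the primary Treg count, by contrast, are defined as changes from baseline.

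**Analysis.** Section 19.5 states: "Statistical analysis will be by student t-test (unpaired) or Mann-Whitney U test". The sentence stands under the primary-outcome heading. The same section gives a chi-square test for categorical data, although the primary endpoint is a cell count, so it appears to reach beyond that endpoint. Section 19.6, on secondary outcomes, names no test, model or covariate. Covariate adjustment appears nowhere in the supplied text. Section 19.3 refers to an SAP for full details, and no separate SAP text was supplied.

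**Baseline data.** Section 19.3 lists HOMA-IR among the baseline biochemical parameters and donor age among the transplant details, both as continuous variables. Sections 13.7.1 and 13.7.2 place fasting c-peptide and glucose at Visit 1, within 24 hours after transplant. Section 13.7.2 lists these bloods ahead of randomisation and dispensing.

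**Size.** Section 19.1 sets "n=25 in each arm" and explains that "the numbers were chosen as this was felt to be feasible given the resources of the site". It gives no effect size, standard deviation or power. Sections 13.4.1 and 13.4.2 mention no stratification.

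**The concern.** Section 11.5 asks whether the arms differ in insulin resistance. The patient's own starting HOMA-IR is the obvious candidate to explain part of the spread at month 3. It is already recorded, and the stated analysis leaves it out. Because the sample size rests on feasibility, the choice of analysis is one of the few remaining ways to narrow the confidence interval. The pilot is also meant to supply data for planning a larger trial, and a narrower interval serves that purpose.

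What is at stake is the width of the interval for a secondary endpoint. The primary conclusion is not affected.

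**Working it through.** **Inputs from the documents.** 25 per arm, 50 in total (19.1); significance at P below 0.05 (19.5), taken as two-sided because sidedness is not stated; unadjusted two-group test (19.5).

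**Assumed input.** The correlation rho between the covariate and the outcome within arms. For HOMA-IR it applies on the log scale. The documents give no value, so 0 to 0.7 is shown.

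**Benchmark.** There is no power calculation to reproduce. For 25 per arm the difference detectable with 80% power is (1.96 + 0.84) x sqrt(2/25) = 0.79 SD by the normal approximation, or 0.81 SD by the t distribution with 48 degrees of freedom.

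**Effect of adjustment.** With one covariate and N = 50, the variance of the adjusted difference relative to the unadjusted one is

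(1 - rho²) x (1 + 1/46) = (1 - rho²) x 47/46.

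For example, at rho 0.5 it is 0.75 x 1.0217 = 0.77. Relative interval width is the square root of this factor, and the equivalent number per arm is 25 divided by it. Power and detectable difference use the noncentral t with 47 degrees of freedom (48 unadjusted). The 0.6 SD effect is illustrative.

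| Analysis | Variance factor | Interval width | Acts like, per arm | Detectable at 80% power | Power at 0.6 SD |
|---|---|---|---|---|---|
| Unadjusted | 1 | 1 | 25 | 0.81 SD | 55% |
| ANCOVA, rho 0 | 1.02 | 1.01 | 24.5 | 0.82 SD | 54% |
| ANCOVA, rho 0.3 | 0.93 | 0.96 | 26.9 | 0.78 SD | 58% |
| ANCOVA, rho 0.5 | 0.77 | 0.88 | 32.6 | 0.71 SD | 66% |
| ANCOVA, rho 0.7 | 0.52 | 0.72 | 48.0 | 0.58 SD | 82% |

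Simulation with 6,000 trials per value gave variance ratios of 1.02, 0.93, 0.77 and 0.53, in agreement.

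**Break-even.** Setting the factor to 1 gives rho² = 1/47, so rho is about 0.15. Below that, adjustment costs at most about 2% of variance.

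**Missing baseline values.** The 2% limit holds only if no patient is dropped. Suppose, as an assumption, that 5 of 50 lack a fasting baseline.

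- Complete-case ANCOVA: the factor is (1 - rho²) x (42/41) x (50/45), which is 1.14 at rho 0. Break-even needs rho² = 1 - (45/50) x (41/42) = 0.121, so rho is about 0.35.
- Filling the gaps with the overall baseline mean keeps all 50. If the gaps are unrelated to the values, the covariate then explains about 0.9 x rho² of the variance, and the factor is (1 - 0.9 rho²) x 47/46. At rho 0.5 that is 0.775 x 1.0217 = 0.79. Break-even is rho = sqrt(1/(47 x 0.9)), still about 0.15.

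**A change score is not a substitute.** Its variance relative to the month-3 value is 2(1 - rho): 1.40, 1.00 and 0.60 at rho 0.3, 0.5 and 0.7. It does worse than the bare follow-up value whenever rho is below 0.5.

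**The case against.** **The unadjusted analysis is inferred for this endpoint.** The test sentence is in 19.5, and 19.6 names none. Applying it to HOMA-IR is the natural reading because no other test is given. This stands as a caveat: an adjusted model in a separate SAP would answer the point.

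**Unadjusted comparison is not biased.** A reader might infer that, without stratification, chance imbalance in baseline HOMA-IR distorts the result. With 25 per arm the chance difference in a baseline variable has a standard error of sqrt(2/25) = 0.28 SD, which at rho 0.5 moves the outcome difference by a typical 0.5 x 0.28 = 0.14 SD. Randomisation makes that shift equally likely in either direction, and the unadjusted interval already allows for it. ANCOVA removes it and so narrows the interval; it does not correct an error.

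**Timing may weaken the baseline.** Visit 1 eGFR is a poor covariate because it is taken within 24 hours of transplant. Baseline HOMA-IR comes from the same bloods. Section 9.1 says that immunosuppressive drugs raise glucose, that insulin clearance changes as renal function improves, and that these effects are strongest early. This stands: rho may be low and the gain small.

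**Donor age is not shown to be prognostic.** A reader might infer that leaving it out of the eGFR comparison loses known precision. Section 19.3 lists it as a baseline descriptor beside ischaemia times, extended-criteria status and HLA mismatch. Nothing in the documents says that it predicts eGFR, or how strongly.

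**This is a pilot with no power claim.** HOMA-IR and month-3 eGFR are secondary, and month-12 eGFR is exploratory. That limits the priority of the point but does not remove it.

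**Conclusion.** The point holds as a low-cost improvement in precision for month-3 HOMA-IR. The supplied text names only an unadjusted test for continuous data and leaves a collected baseline value unused. Adjustment would multiply the variance by 0.93 to 0.52 for assumed correlations of 0.3 to 0.7, and by 1.02 if the baseline is uninformative.

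A reader might take the last row of the table, 55% to 82% power, as the expected benefit. The documents do not support that: they give no correlation, and the early post-transplant baseline argues for the lower part of the range. At rho 0.3 the gain is about three percentage points of power for a 0.6 SD effect. Nor can the precision be called free, since there is a small cost below rho of about 0.15 and a larger one if patients with missing baselines are dropped.

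For eGFR, adjustment for a donor variable is an option for the sponsor and rests on an assumption from outside the documents.

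**What to change.** In section 19.6, pre-specify for month-3 HOMA-IR:

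- ANCOVA of log month-3 HOMA-IR on treatment and log baseline HOMA-IR, reporting the adjusted ratio with its 95% confidence interval;
- baseline taken from the Visit 1 sample drawn before the first dose;
- missing baseline values filled with the overall mean of log baseline across both arms, so that no patient is dropped for a missing covariate;
- the unadjusted or Mann-Whitney result as a sensitivity analysis.

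Optionally, for month-3 and month-12 eGFR, name one recorded donor variable, such as donor age, as the single covariate, and state that its prognostic value is assumed. Fix the choice before unblinding, so that covariates are not selected on results.

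No new measurement or patient is needed. Section 19.6 is protocol text, so the change goes through the amendment process in section 27.1. That section needs rewording in any case, because it states the null hypothesis for secondary endpoints in terms of the primary endpoint. The statistical downside is about 2% of variance if the covariate proves uninformative.

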9.0 Introduction

9.1 Background

Renal Transplantation and glucose control

Type 2 diabetes is the most common cause of end-stage renal failure in the UK. Kidney transplantation is widely held to be the optimal form of renal replacement therapy for patients with end-stage renal disease, leading to a longer survival and improved quality of life in patients receiving a renal transplant compared to those that remain on dialysis (Reese et al, 2015).

However transplantation leads to a higher glucose burden in patients. This has been associated with acute rejection, sepsis and worse outcomes, and patients frequently have to increase their anti-diabetic medication in the early post-transplant period.

One reason for this is that immunosuppressive medications (glucocorticoids and calcineurin inhibitors) can lead directly to hyperglycaemia. In addition, as renal function improves, there is greater renal clearance of anti-diabetic agents and endogenous insulin leading to a reduced potency of these medications. These effects are most pronounced within the early post-transplant period, as this is the period when the immunosuppressive burden is the strongest and the changes in renal function most marked.

The role of Glucokinase in glucose control

Glucokinase is an enzyme which has two effects to lower glucose. In the pancreas, beta cells control insulin secretion. In pancreatic beta cells glucokinase converts glucose to glucose-6-phosphate, which is a rate-limiting step in the secretion of insulin; as such, increased glucokinase activity leads to more insulin secretion. Secondly, in the liver, glucokinase increases hepatic uptake of glucose (Scheen, 2018). Defective glucose-induced insulin secretion and increased hepatic glucose output are of the hallmarks of type 2 diabetes. Because of these effects, glucokinase activators have been promising therapeutics for type 2 diabetes for almost two decades.

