11.5 Objectives and Endpoints Summary

Objective	How objective measured	Outcome
Examine the effect of AZD1656 on Treg cell migration	Change in peripheral Treg population between randomisation and month 3 measured by mean change in Treg cell number between baseline and 3 months using FACS analysis.	Does AZD1656 lead to enhanced migration as demonstrated by a fall in peripheral Treg population over time compared to placebo?
Examine the effectiveness of AZD1656 on diabetic control	Change in HbA1c between baseline and month 3 visit, HOMA-IR at month 3, descriptive change in anti diabetic medication dose/need for additional anti-diabetic therapy.	Is there a difference between placebo and IMP on diabetic control/insulin resistance?
To investigate the effect of AZD1656 on renal transplant function	Renal function (eGFR CKD EPI) measured at 3 months and 12 months.	Is there a difference between AZD1656 and placebo treated patients' renal function at 3 and 12 months?
To determine the safety of AZD1656 to control diabetes post- transplant.	Patient and graft survival, number and type of AE (hypoglycaemic episodes, infective episodes), number and type of SAE, rejection rates (defined as incidence of biopsy proven acute rejection)	Is there a difference between placebo and AZD1656 treated groups in terms of number of AE, SAE, renal function and rejection rates?
Effect of AZD156 on Treg cell infiltration in renal transplant tissue	Change in Treg staining on renal biopsies collected as standard of care at implantation and 3 months post transplant.	Is there a difference between placebo and AZD1656 treated groups in terms of change in Treg cell infiltration between baseline and 3 month transplant biopsy?

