13.7 Trial Schedule

13.7.1 Schedule of Assessment (in Diagrammatic Format)

Schedule of									Data
visits	Screening	Visit 1	Visit 2	Visit 3	Visit 4	Visit 5	Visit 6	Visit 7	review
Day/Month	Before or	Randomisati	week 1	week 2	week 4	week 8	week 12	2 weeks after	1 yr post
	within 24h	on up to 24h	post	post	post	post	post	stopping	transplan
	post	post	randomisat	randomisat	randomisat	randomisat	randomisat	study	+/- 2
	transplant	transplant	ion (+/- 3	ion (+/- 3	ion (+/- 3	ion (+/- 1	ion (+/- 1	medication	, – weeks
	transplant	transpiant	days)	days)	days)	week)	week)	(+/- 1 week)	WEEKS
Informed								(1) = 110011	
Consent	Х								
Inclusion/									
exclusion									
criteria	Х	x							
Negative									
pregnancy test	х	x	х	х	x	x	x	x	
pregnancy test	^	^	^	^	^	^	^	^	
Demographics	х								
Transplant									
data		х							
Medical									
	Y								Х*
history	x								X*
Randomisation		x							
Study drug									
dispense		x							
Drug									
accountability			х	х	х	х	х		
Dhusiaal									
Physical									
examination		X	X	X	x	x	X	X	
Weight		х	х	х	х	х	х	х	Х*
Vital signs		x	х	х	x	x	x	х	Х*
Concomitant									
medication	X	X	X	X	X	X	X	X	X*
Laboratory									
bloods**		x	x	x	x	x	x	x	Х*
Placed for Two									
Blood for Treg									
quantification		x	x				x	x	
AE assessment		X	X	X	x	x	x	X	Х*
End-point									
assessment							x		

*At this review, the patient's medical records will be reviewed and their clinical data extracted to include:
Graft function as measured by eGFR and serum creatinine
Episodes of rejection
Episodes of infection
Diabetic control measured by HbA1c
Vital signs
Weight
Current medication and anti-diabetic medication regimen

**Laboratory bloods: including fasting c-peptide, cholesterol and serum glucose; serum urea and electrolytes (including creatinine), albumin, alkaline phosphatase (ALP), bilirubin, alanine aminotransferase (ALT), bone profile and C-reactive protein; haemoglobin and HbA1c; and serum save +/- blood for peripheral Tregs as per protocol. The serum save will be taken and processed in keeping with normal protocols but will be used for functional assays to measure the activity of the Tregs at different time points.

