13.7.2 Trial assessments

Screening visit

Informed consent Inclusion/exclusion criteria

Documentation of a negative pregnancy test from pre-transplant care

In women of childbearing potential: defined as women following menarche until becoming post-menopausal, unless permanently sterile. Permanent sterilisation methods include hysterectomy, bilateral salpingectomy and bilateral oophorectomy. A postmenopausal state is defined as the absence of menses for 12 months without an alternative medical cause.

Medical history

Demographic data

Concomitant medication

Visit 1 - to occur within 24 hours post-transplant

Inclusion/exclusion criteria

Transplant data

Documentation of a negative pregnancy test

Concomitant medication

Targeted physical examination

Adverse event reporting

Laboratory bloods: including fasting c-peptide, cholesterol and serum glucose; serum urea and electrolytes (including creatinine), albumin, alkaline phosphatase (ALP), bilirubin, alanine aminotransferase (ALT), bone profile and C-reactive protein; haemoglobin and HbA1c; and serum save. Results from bloods that have been taken as part of routine care may also be included on the case record forms.

20ml of blood will also be taken for peripheral Treg quantification.

Vital signs recording

Weight

Randomisation

Study drug dispense

In addition, the renal biopsy specimen collected as per clinical care at time of biopsy will be stained for Treg cell markers.

Visit 2 (1 week post randomisation +/- 3 days))

Check drug adherence Concomitant medication Documentation of a negative pregnancy test Targeted physical examination Weight Vital signs recording

Fasting blood tests: including fasting c-peptide, cholesterol and serum glucose; serum urea and electrolytes (including creatinine), albumin, alkaline phosphatase (ALP), bilirubin, alanine aminotransferase (ALT), bone profile and C-reactive protein; haemoglobin and HbA1c and serum save. Results from bloods that have been taken as part of routine care may also be included on the case record forms. 20ml of blood will also be taken for peripheral Treg quantification.

Adverse event reporting

Visit 3 (2 weeks post randomisation +/- 3 days)

Activities as per visit 2 with exception of blood collection for Treg quantification

Visit 4 (4 weeks post randomisation +/- 3 days)

Activities as per visit 3

Visit 5 (8 weeks post randomisation +/- 1 week)

Activities as per visit 3

Visit 6 (12 week post randomisation +/- 1 week)

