14.2 Sample Collection/Labelling/Logging

Samples will be collected by the research nurse or trained phlebotomist as per standard of care.

Samples will be labelled with patient identification and sent to the local labs as per routine care and the results logged on the pathology system and transcribed to the CRF.

The only samples that will be sent to the local lab, which are not part of routine care, are for serum C-peptide.

Volume of samples to be collected:

The total volume of blood which will be taken on top of routine care is:

1 table-spoon (approximately 20ml) of blood per clinic visit (4x 6ml samples of blood) in lithium heparin tubes provided locally.

In addition, 20ml of blood will be taken at visit 1, 2, 6 and 7 for Treg quantification via FACS. This sample will be taken to the Royal London Immunology laboratories by members of the study team for processing.

Any biopsy material will be processed and stored as part of routine clinical care.

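### Month-3 HOMA-IR almost certainly rests on C-peptide, so a between-arm difference in it should not by itself be reported as a difference in insulin resistance

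*Combined protocol and SAP*

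**What the plan says.** Section 11.3.2 names the secondary endpoint as "Insulin resistance: HOMA IR measurement at month 3". Section 11.5 uses it, with HbA1c and anti-diabetic medication, to answer "Is there a difference between placebo and IMP on diabetic control/insulin resistance". HOMA-IR is also a listed baseline variable in section 19.3.

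No formula or HOMA version is stated. The only hint is a letter about HOMA software in the reference list.

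The schedule in 13.7.1 gives "Laboratory bloods: including fasting c-peptide, cholesterol and serum glucose". Section 13.7.2 gives "Fasting blood tests: including fasting c-peptide, cholesterol and serum glucose" for visit 2 and carries the same panel to visit 6 (week 12). Insulin is in neither list, nor among the biochemical variables in 19.3. Section 14.2 adds: "The only samples that will be sent to the local lab, which are not part of routine care, are for serum C-peptide". The stored serum "will be used for functional assays to measure the activity of the Tregs at different time points" (13.7.1), so it is not set aside for an insulin assay.

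The only test named for continuous data is an unpaired t-test or Mann-Whitney test at P<0.05. It stands in 19.5, under the primary outcome. Section 19.6 adds only a generic null hypothesis.

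**The concern.** Fasting C-peptide reflects secretion and clearance as well as insulin resistance. Three things other than resistance could move a C-peptide-based index in this trial:

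- **Graft function.** Section 9.1 says that "as renal function improves, there is greater renal clearance of anti-diabetic agents and endogenous insulin". C-peptide is not named there. That it is also cleared by the kidney is general physiology. Section 11.5 asks whether eGFR differs between the arms at 3 months.
- **Exogenous insulin.** Insulin-treated patients are not excluded (12.1, 12.2), and section 9.2 lets clinicians change anti-diabetic treatment after randomisation. Injected insulin suppresses C-peptide (again general physiology), so the index reads low in a patient who may be quite resistant.
- **The drug itself.** Section 9.1 says that increased glucokinase activity increases insulin secretion. C-peptide could therefore change on AZD1656 without any change in resistance.

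Randomisation balances these at entry in expectation. It does not prevent differences that arise afterwards. As planned, such a difference would be reported under the insulin resistance label and could inform the larger trial that section 19.1 has in view.

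**Working it through.** The documents give no effect size, SD, power or formula for HOMA-IR, so there is no stated figure to reproduce. The 25 per arm (19.1) was chosen for feasibility. Every physiological size below is an assumption.

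**1. Graft-function route.** Assume C-peptide = secretion / clearance, with a share s of clearance renal at GFR 100. At equal secretion and glucose the index is proportional to 1 / [(1 - s) + s × eGFR/100]. For an arm at eGFR 50 against one at eGFR 60:

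| s | Denominator at 60 | Denominator at 50 | Index, 50 relative to 60 |
|---|---|---|---|
| 0.50 | 0.80 | 0.75 | +6.7% |
| 0.70 | 0.72 | 0.65 | +10.8% |
| 0.85 | 0.66 | 0.575 | +14.8% |

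The arm with better graft function reads lower. If that arm is AZD1656, it looks like a benefit.

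**2. Insulin-use route.** Let d be the excess proportion of insulin users on placebo and u the suppression of C-peptide in a user. The mean log shift, active minus placebo, is -d × ln(1 - u).

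- d = 0.1, u = 0.2: 0.022, or +2.3%
- d = 0.3, u = 0.5: 0.208, or +23.1%

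Here the drug looks worse.

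**3. Against sampling error.** SE of the arm difference in ln(HOMA-IR) = SD × √(2/25). For an assumed SD of 0.5 to 0.7 this is 0.141 to 0.198. The eGFR shift is ln(1.067) = 0.065 to ln(1.148) = 0.138, so it stays below one SE. The insulin shift exceeds one SE only towards the top of its range.

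**4. How often the planned t-test would reject when true resistance is equal.** Simulation: 20,000 runs, 25 per arm, two-sided 0.05, log-SD 0.5, 40% suppression, log-SD of eGFR 0.35, and a 50% renal share taken at the placebo arm's typical eGFR.

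| Month-3 state, active relative to placebo | Apparent difference | Rejection |
|---|---|---|
| Arms equal | 0% | 4.9% |
| eGFR 20% higher | -9% | 8.6% |
| Insulin use 30% vs 50% | +11% | 9.5% |
| Insulin use 20% vs 50% | +17% | 15.4% |
| eGFR 20% higher and insulin use 30% vs 50% | +1% | 4.5% |
| eGFR 15% lower and insulin use 30% vs 50% | +20% | 18.6% |

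**5. What adjustment can and cannot do.** A second simulation assumed s = 0.70 and log-SD 0.5, again with equal true resistance.

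- With eGFR 20% higher on drug (60 vs 50), the spurious log shift is ln(0.65/0.72) = -0.10. Adjusting for same-visit eGFR removes it: rejection falls from 9.9% to 5.2%, and the SE from about 0.164 to 0.148.
- With insulin added after randomisation (30-point excess on placebo, 50% suppression), the shift is 0.208 unadjusted and 0.212 after adjustment that includes insulin use at entry. Both analyses are significant in 17% of runs. Entry use is balanced by randomisation and carries no information on insulin added later.

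**The case against.** Several points on the other side stand.

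- **The missing assay is an inference.** The panels are introduced as non-exhaustive, and section 13.7.2 allows routine-care results to be used. Section 19.3 also refers to a SAP for full details, and no fuller HOMA rule appears in the text available. A reader might infer that C-peptide is the only possible input. The lists and section 14.2 make it very likely, not certain.
- **The protocol does not say that C-peptide depends on graft function or on injected insulin.** Section 9.1 speaks of endogenous insulin only.
- **The protocol does not predict the imbalance.** A reader might infer that it expects better eGFR on drug. Section 9.3 hypothesises less reperfusion injury, seen in delayed graft function, and more Treg localisation. Section 11.5 only asks whether eGFR differs. Nothing says that placebo patients will need more insulin.
- **Part of the context is already reported.** Month-3 eGFR and anti-diabetic medication dose are themselves secondary endpoints.
- **Adjusting for month-3 eGFR conditions on a post-randomisation outcome**, and can remove part of a real effect.

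None of this supplies a definition of the index or a limit on what may be concluded from it. Planned eGFR and medication summaries help a careful reader, but they do not stop the difference being labelled insulin resistance.

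**Conclusion.** The point holds as a limit on interpretation. Month-3 HOMA-IR almost certainly rests on fasting C-peptide and glucose. If the arms differ at month 3 in eGFR or insulin use, the unadjusted comparison can show a difference that is not insulin resistance. The size is roughly 7-15% for a 10-point eGFR gap and 2-23% for an excess of insulin users on placebo, the latter opposing better graft function on drug. These ranges depend wholly on the assumed renal share, suppression and insulin-use gap.

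Two stronger readings are not supported. One is that the planned test has an inflated error rate as it stands: with arms alike in eGFR and insulin use it rejects 4.9% of the time, and the two distortions can offset. The other is that agreement between an unadjusted and an adjusted analysis would justify the insulin resistance label: insulin added after randomisation passes through both.

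This concerns one of nine secondary endpoints in a pilot. The primary Treg result is unaffected. The change is still worth making, because it alters what the trial may conclude and needs no new data.

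**What to change.** 1. In 11.3.2, 11.5 and 19.6, name the endpoint a C-peptide-based HOMA index and state the formula or software version and its inputs. If insulin is in fact to be measured, say where; injected insulin would still complicate the reading.
2. State that a between-arm difference in this index alone will not be reported as a change in insulin resistance.
3. Keep the planned comparison of arms and adjust it for insulin use at entry, fitted as a linear model of ln(HOMA-IR), for precision only. Entry medication is already recorded.
4. Add one supportive analysis of ln(HOMA-IR) with same-visit eGFR as a covariate. State that eGFR is post-randomisation and that the adjustment may remove part of a real effect.
5. Show the index by month-3 insulin use (yes/no) within each arm, beside the planned eGFR and anti-diabetic medication summaries.
6. Do not treat agreement between the analyses in items 3 and 4 as grounds for the insulin resistance label.

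The cost is a paragraph of plan wording, one regression and one table, all from data already scheduled. No extra sample or change in patient care is needed. The price is a more modest claim: section 11.5 would be answered on diabetic control, with the index as supporting description.
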